## 10 SAFETY MONITORING

### 10.1 INDEPENDENT DATA MONITORING COMMITTEE

The iDMC, composed of relevant experts (pediatric rheumatologist, pediatric onco-hematologist with experience in HLH, pediatric immunodeficiency/infectious disease specialist, bio-statistician and a specialist in ethics), will oversee the study, with particular regard to the evaluation of safety parameters and benefit/risk profile of emapalumab, reviewing all data generated on an ongoing basis with the aim to ensure that patients are not exposed to unnecessary risks. Some of the iDMC members have been already

involved in the oversight of the ongoing emapalumab studies. Please refer to [Section 10.5.1](#) for further details on the iDMC.

## 10.2 DESCRIPTION OF SAFETY PARAMETERS

Evaluation of emapalumab tolerability and safety will be based on the following parameters:

- Adverse events (AEs), with special attention being paid to potential infusion related reactions (IRRs), (i.e events occurring during or within 24 hours post infusion) and to the occurrence of infections, particularly with pathogens associated with lack of IFN $\gamma$  biological activity (due to emapalumab mode of action).
- Laboratory parameters, as described in [Section 8.4](#)
- Vital signs, as described in [Section 8.3.1](#)
- Physical examination with particular attention paid to evolution of signs and symptoms present at baseline, and to any emergent new signs or symptoms (see [Section 8.3.2](#) for more details).

## 10.3 RECORDING AND REPORTING SAFETY PARAMETERS

### 10.3.1 Adverse events

Adverse events (AEs) are defined as any undesirable experience occurring to a subject during the study, whether or not considered related to the IMP. All AEs reported by the patients or his/her relatives or observed by the Investigator or his staff during the clinical study from the signature of the ICF up to and including the EoS visit will be reported on the AE data collection form.

Medical conditions present at screening (before ICF signature) should be recorded in the medical history section of the CRF.

All AEs will be reported in the appropriate section of the CRF.

An AE which occurs between start of screening visit (after ICF signature) and start of first IMP administration will be considered as a pre-treatment AE.

Any AE that occurs after the start of the first IMP administration will be considered in the study as Treatment Emergent Adverse Event (TEAE).

However, if a pre-existing medical condition recorded in the medical history worsens (clinically significant change in intensity or frequency), it must be recorded as an AE in the CRF and, depending on the time of its occurrence, will be considered as a pre-treatment AE or a TEAE. If a medical condition, recorded as a pre-treatment AE, worsens it will be recorded in the CRF as a separate TEAE.

For each AE, the following will be assessed and recorded: intensity, relationship to the IMP, action taken regarding the IMP, any treatment received for the event and outcome of AE to date.

Intensity of AEs will be graded on a three-points scale (mild, moderate, severe) using the modified WHO (World Health Organization) toxicity scale (Grade 3 and 4 are considered to be the severe grade). If AE severity cannot be assessed by this scale, assessment by the Investigator should be made using the following definitions:

- Mild: discomfort noticed but no disruption of normal activity,
- Moderate: discomfort sufficient to reduce or affect normal daily activity,
- Severe: inability to work or perform normal daily activity.

For a given AE, the assessment of its intensity should reflect the highest grade (on the 3 points scale mentioned above) reported during its course (except when the intensity of a pre-treatment AE increases after treatment initiation, as indicated above).

The relationship of the AE to the IMP will be assessed by the Investigator using a “Yes/No” classification. A “Yes” relationship infers that there is a reasonable possibility of causal relationship between the AE and IMP. The expression “reasonable possibility” is meant to convey that there are facts, evidence or arguments to suggest a causal relationship. Conversely, a “No” relationship infers that there is no reasonable possibility of causal relationship between the AE and IMP. Usually it implies that other possible causes have been identified.

In this study emapalumab is the only IMP.

Abnormal laboratory findings should be reported as AEs if requiring specific treatment. Exception to this is the onset of any new or worsened abnormal laboratory findings [e.g. cytopenias (all three lines), abnormalities denoting liver dysfunction, coagulopathy, abnormal ferritin, fibrinogen and triglyceride levels] indicative of an HLH/MAS reactivation or worsening: in this specific instance, the reactivation or worsening of HLH/MAS must be reported as the AE and not the abnormal laboratory findings, even if requiring intervention.

If an abnormal laboratory finding leads to a new diagnosis, this diagnosis should be reported as AE (e.g. hyperglycaemia leading to diagnosis of diabetes mellitus).

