### 1.1.3 Clinical Data

*Note to the reader: in order to reflect the information available at the time the study was initiated this section is not being updated. Please refer to the most current Investigator's Brochure to ensure awareness of the data that served as basis for the approval of emapalumab in the US for the treatment of adult and pediatric (newborn and older) patients with pHLH with refractory, recurrent or progressive disease or intolerance with conventional HLH therapy and to ensure awareness of all available clinical data.*

A Phase 1 randomized double-blinded placebo-controlled single ascending dose study in 20 healthy adult volunteers investigating the safety, tolerability and pharmacokinetic profiles of single intravenous (i.v.) administrations of emapalumab was conducted between September 2011 and April 2012. During this study a total of 14 subjects received increasing doses of 0.01, 0.1, 1, and 3 mg/kg emapalumab (3, 3, 4, and 4 subjects, respectively), while 6 subjects received placebo.

The pharmacokinetics (PK) analysis of emapalumab revealed the expected profile for an IgG1 with a half-life of approx. 22 days, a slow clearance ( $\leq 0.007$  L/h) and a low volume of distribution ( $< 6$  L on average).

All emapalumab infusions were uneventful.

A similar incidence of commonly reported infections (e.g., upper respiratory tract infections) was observed after administration of emapalumab and in subjects who had received placebo.

A Herpes Zoster (HZ) infection was reported in one subject (██████████), 14 days after his infusion of 3 mg/kg of emapalumab. This event was assessed as related to the emapalumab infusion and considered as serious (medically significant) in the context of a Phase 1 study in healthy volunteers (HVs). Its intensity was moderate and its course normal under antiviral therapy. The subject recovered with no sequelae.

An increased susceptibility to HZ infections in patients having developed auto-antibodies against IFN $\gamma$  (Browne SK 2012) or having received ustekinumab (a mAb which decreases IFN $\gamma$  production by inhibiting the p40 subunit of IL-12) has been described in the literature (Failla V 2011).

In conclusion, the infusion of emapalumab was well tolerated and the effects observed during the 8 week monitoring after drug infusion did not reveal any serious or unexpected off-target safety or immunogenicity concerns.

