### 3.4 FOLLOW-UP PERIOD

All patients who have received at least one dose of emapalumab will be monitored after the last administration of emapalumab. A short-term follow-up of at least 4 weeks has to be performed under the current protocol, therefore should emapalumab treatment in a given patient need to be prolonged beyond 4 weeks, additional visits will be performed weekly until completion of the 4-week short-term follow-up.

The last visit for a given patient under the NI-0501-06 study will normally be on SD56 (except in case of prolongation of emapalumab treatment beyond 4 weeks, as above described).

Afterwards all patients will be asked to enter a long-term follow-up study, NI0501-05, to allow long-term outcome and safety surveillance, and to monitor emapalumab elimination profile.

In the event that additional monitoring of emapalumab concentrations is required (e.g., emapalumab serum levels still measurable at EoS) and cannot be performed in the context of the long-term follow-up study, unscheduled visits will have to be performed beyond SD56, until serum emapalumab levels are no longer detectable. These measurements should occur not less than every two weeks.

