#### 4.1.1 Inclusion Criteria

1. Patients of both genders,
2. For sJIA patients: Confirmed sJIA diagnosis. For patients presenting with MAS in the context of the onset of sJIA, high presumption of sJIA (as per [Appendix A](#)) will suffice for eligibility. For AOSD patients: confirmed AOSD diagnosis as per Yamaguchi criteria ([Appendix E](#))
3. A diagnosis of active MAS confirmed by the treating rheumatologist, having ascertained the following:
  - Febrile patient presenting with:*
    - Ferritin > 684 ng/mL
  - and any two of:*
    - Platelet count  $\leq 181 \times 10^9/L$
    - AST levels > 48 U/L
    - Triglycerides > 156 mg/dL
    - Fibrinogen levels  $\leq 360$  mg/dL(see [Appendix B](#)).
4. An inadequate response to high dose i.v. glucocorticoid treatment administered for at least 3 days as per local standard of care (including but not limited to pulses of 30 mg/kg PDN on 3 consecutive days).

High dose i.v. glucocorticoid should not be lower than 2 mg/kg/day of PDN equivalent in 2 divided doses ( or at least 60 mg/day in patients of 30 kg or more). In case of rapid worsening of the patient's condition and/or lab parameters, inclusion may occur within less than 3 days from starting high dose i.v. glucocorticoids.
5. Tocilizumab, TNF inhibitors and canakinumab, if administered, have to be discontinued before emapalumab initiation.
6. Informed consent provided by the patient (as required by local law), or by the patient's legally authorized representative(s) with the assent of patients who are legally capable of providing it, as applicable.

7. Having received guidance on contraception for both male and female patients sexually active and having reached puberty:

Females of child-bearing potential require use of highly effective contraceptive measures (failure rate of less than 1% per year) from screening until 6 months after receiving last dose of the study drug.

Highly effective contraceptive measures include:

- Sexual abstinence
- Hormonal contraceptives: combination or progesterone only
- Intrauterine methods: intrauterine devices or systems
- Bilateral tubal occlusion
- Vasectomised partner

Males with partners(s) of child-bearing potential must agree to take appropriate precautions (such as sexual abstinence, barrier contraception, vasectomy) to avoid fathering a child from screening until 6 months after receiving last dose of the study drug.

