## 8.8 PHARMACOKINETIC/PHARMACODYNAMIC ASSESSMENTS

### 8.8.1 Pharmacokinetics

Serum samples for PK analysis will be collected at the visits indicated in the SoA (Table 1 and Table 2). In case of need for prioritization of blood analysis (considering weight and health status of the patient), laboratory safety parameters (which would be done as normal disease monitoring) may need to be prioritized over samples for PK assessments, that in turn will be prioritized over biomarkers exploratory parameters.

On the days of infusion, PK samples should be collected before and after (between 15 and 30 minutes after) the infusion.

After the first emapalumab infusion, PK samples will be also collected on SD1 (around 24 hrs. post-infusion) and SD2 (around 48 hrs. post-infusion). Additionally, PK samples will be collected on SD5 (around 48 hrs. after the second emapalumab infusion).

After completion of emapalumab infusions, samples for PK assessment will be collected until serum emapalumab concentration are no longer detectable (or until consent is withdrawn), as indicated in the SoA until the EoS visit. In case of CNS involvement, if lumbar puncture is performed for diagnostic and/or therapeutic purposes, PK analysis in CSF samples may be performed.

Details on sample preparation and handling will be described in a separate laboratory manual.

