### 10.3.2 Serious Adverse Events

An adverse event is considered serious if it:

- results in death (note: death is an outcome, not an event);
- is life-threatening; (note: the term "life-threatening" refers to an event in which the patient was at immediate risk of death at the time of the event; it does not refer to an event which could hypothetically have caused a death had it been more severe);
- requires in-patient hospitalization or prolongs an existing hospitalization;
- results in persistent or significant disability/incapacity;
- is a congenital anomaly/birth defect;
- is an important medical event that may not result in death, be life-threatening, or require hospitalization but may be considered serious when, based upon appropriate medical judgment, they may jeopardize the patient and may require medical or surgical intervention to prevent one of the outcomes listed above. Examples of such medical events include allergic bronchospasm requiring intensive treatment in an emergency room or at home, blood dyscrasias or convulsions that do not result in inpatient hospitalization, or the development of drug dependency or drug abuse.

For the purposes of this study, the following will not be considered as serious adverse events:

- Elective hospitalizations or surgical procedures that are a result of a patient’s pre-existing condition(s) which has (have) not worsened since receiving IMP. Such events should still be recorded as adverse events in the CRF;
- Hospitalization as requested per protocol for emapalumab infusion and study visits.

Any serious adverse event (SAE) that occurs during the course of the study, irrespective of the treatment received by the subject and regardless of causality to the study drug, must be communicated by the Investigator to Sobi AG, by fax or electronic transmission, within 24 hours of awareness.

For the initial SAE report, the Investigator should report all available case details concerning the patient and the event, using the Sobi AG SAE reporting standard form provided to the Investigators.

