### **10.4.2 Pregnancy**

In the event that a pregnancy occurs during the trial course, it must be reported to Sobi AG within 24 hours of awareness. This includes pregnancies occurring in partners of male enrolled patients. All information pertaining to the pregnancy should be reported using the Sobi AG Pregnancy form provided to the investigators. Pregnancies should be followed until conclusion to obtain outcome information.

Occurrence of a pregnancy in a study participant will preclude any further IMP administration.

If the patient is withdrawn from the study, the assessments presented in the Schedule of Assessments for EoS are to be performed (see [Section 8.9](#)).

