#### 10.5.2.3 Risk minimization measures

In view of the expected benefits and previous experience gathered with patients exposed to emapalumab the above listed risks are considered to be manageable in this patient population, if adequate minimization measures are put in place. An overview of specific measures to minimize the subject's risk is provided below:

- Study designed with rheumatologists experienced in the treatment of sJIA and MAS, forming the SSC.
- Patients are hospitalized in specialized centers for the treatment of MAS, and therefore with all necessary emergency assistance equipment.
- Inclusion/exclusion criteria: patients with malformations or severely altered functions (either due to the disease stage or to a concomitant disease), as well as patients with evidence of patent or latent TB infections or active mycobacteria, *Shigella*, *Salmonella*, *Campylobacter*, *Histoplasma Capsulatum* or *Leishmania* infections, will not be included in the study (for details see Section 4.1).
- Although unlikely to be observed based on preliminary results gathered from patients treated with emapalumab up to 10mg/kg, Infusion Related Reactions (IRRs) will be detected and managed in due time through patients' monitoring during and after drug infusions. Each of the specialized centers will have physicians adequately trained in IRR management.

- Recommendations on prophylaxis for Herpes Zoster virus for all patients and Tuberculosis for a defined subpopulation (see [Section 6.2](#)) in the protocol to avoid occurrence of these infections.
- The monitoring for specific infections, known to be favored by IFN $\gamma$  neutralization, will continue after emapalumab discontinuation as long as serum emapalumab levels are detectable.
- Close monitoring of potential infections through careful physical examination, laboratory parameters, active search for EBV, CMV, Adenoviruses, detection of tuberculosis
- Study safety surveillance by an independent Data Monitoring Committee

The Development Risk Management Plan addresses risks, identify signals for early detection of safety concerns and propose mitigating actions. It will be part of the study documentation shared with Investigators and any relevant third party involved in the study. Stopping rules have been also developed to ensure individual patient safety and determine whether the study should be put on hold or terminated prematurely.

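### AE recording closes at the EoS visit while drug may still be measurable, and no rule says how a new infection found after that visit is recorded

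*Protocol*

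**What the plan says.** **Recording window.** Protocol 10.3.1 has AEs "from the signature of the ICF up to and including the EoS visit will be reported on the AE data collection form". Section 3.4 puts the last visit normally at SD56, later if treatment is prolonged. SAP 3.1 keeps the visit schedule to SD56 when treatment is shortened.

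**Serious events.** Section 10.3.2 covers "Any serious adverse event (SAE) that occurs during the course of the study, irrespective of the treatment received by the subject" and names no last day for the individual patient. Section 3.5 defines the end of the study as the last visit of the last patient.

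**Expected exposure.** Section 1.1.3 gives a "half-life of approx. 22 days" in healthy volunteers. If concentrations still need monitoring after SD56 and the long-term study cannot do it, section 3.4 says that "unscheduled visits will have to be performed beyond SD56, until serum emapalumab levels are no longer detectable", with measurements no less often than every two weeks.

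**Infection measures.** Zoster prophylaxis runs until drug is undetectable, expressly including time after the end of the study (6.2). PCR searches for TB, EBV, CMV and adenovirus run every two weeks while drug is detectable (8.5). Monitoring for infections favoured by IFNγ neutralisation "will continue after emapalumab discontinuation as long as serum emapalumab levels are detectable" (10.5.2.3).

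**Long-term study.** Every treated patient is asked to enter NI-0501-05 (3.4, 3.6). Entry is not a condition of taking part.

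**Two related passages.** Section 8.8.1 has PK samples taken until drug is undetectable, but in the same sentence "as indicated in the SoA until the EoS visit". Contraception is required "from screening until 6 months after receiving last dose of the study drug" (4.1.1), while the pregnancy reporting duty begins "In the event that a pregnancy occurs during the trial course" (10.4.2).

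**The concern.** The protocol ties its infection measures to detectable drug but ties AE recording to a calendar visit. When drug outlasts that visit, sites must go on searching for infection, yet 10.3.1 no longer asks them to record what they find. Read literally, a new non-serious infection found at a required visit after EoS goes unrecorded.

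Infections are singled out in the safety endpoints (7.3). The infection counts in the CSR could therefore cover only part of the exposed period. The analysis is not the obstacle: the SAP definition of a treatment-emergent event (6.1.7) has no end date, so a late event would be counted if it were collected. The gap lies in collection.

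**Working it through.** **1. The plan's own dates.** SD28 + 28 days = SD56, which matches section 3.4. Treatment can stop once two 3 mg/kg infusions have been given, so the earliest last infusion is SD6, and SD56 − SD6 = 50 days.

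**2. The stated half-life.** Section 1.1.3 bounds volume below 6 L and clearance at 0.007 L/h. At those bounds ln 2 × 6 / 0.007 = 594 h = 24.8 days. A value of 22 days needs a volume of 5.3 L, so the stated figure is consistent with them.

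**3. Share left at EoS.** Fraction = 0.5^(days since last dose / half-life). Only the 22-day value is in the documents; the others are assumed, to show the range.

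| Half-life | Left after 28 days | Left after 50 days | Five half-lives, relative to EoS (last dose SD28) |
|---|---|---|---|
| 22 d | 41% (1.27 half-lives) | 21% (2.27 half-lives) | 82 days after |
| 11 d | 17% | 4% | 27 days after |
| 7 d | 6% | 1% | 7 days after |
| 5 d | 2% | 0.1% | 3 days before |

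**4. Amount on board at SD56, linear elimination, 22 days.** Amount = sum of dose × 0.5^((56 − dose day)/22).
- Full course (6 mg/kg, then nine doses of 3 mg/kg; infusion days after SD15 assumed at about SD18, 22, 25 and 28): 21.2 mg/kg at SD28, and 21.2 × 0.414 = 8.8 mg/kg at SD56.
- Shortest course (SD0, SD3, SD6): 6 × 0.171 + 3 × 0.188 + 3 × 0.207 = 2.2 mg/kg at SD56.

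**5. Effect of target-mediated clearance.** Section 5.3 sets VMAX as IFNγ concentration × 1.2 L/h/kg divided by the binding sites per antibody. Assuming two sites, a 150 kDa antibody, one compartment and saturated elimination, 0.1 nM gives 0.1 × 1.2 / 2 = 0.06 nmol/h/kg = 0.216 mg/kg/day. For the full course:
- 0.1 nM throughout: 3.1 mg/kg left at SD56, gone near SD68.
- 0.3 nM throughout: gone near SD40, before EoS.
- Target-mediated clearance ending at SD28 because disease is controlled: 7.1 mg/kg left at SD56 for 0.1 nM, falling to 1.2 mg/kg for 3 nM.

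Neither the half-life in this population nor the assay limit is given, so the day on which drug becomes undetectable cannot be calculated. Sections 3.4 and 6.2 nevertheless foresee measurable drug after EoS.

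**6. Rules that might cover a new event after EoS.**
- 10.3.1: closed at EoS.
- 10.3.2: depends on what the course of the study means. If it ends at the last patient's last visit (3.5), coverage after EoS depends on enrolment order and is least for the last patient. The same section requires every SAE to be entered as an AE in the CRF, where 10.3.1 has closed the window.
- 3.5: follows SAEs already ongoing, not new ones.
- 8.10: unplanned visits may include evaluation of AEs and SAEs. This permits but does not require it, and the unscheduled-visit column of Table 2 marks only vital signs and physical examination.
- NI-0501-05: a separate, voluntary study whose AE rules are not in these documents.

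**7. Pregnancy.** Six months is about 182.6 days. The share of the contraception period after EoS is (182.6 − 28)/182.6 = 85% for a last dose on SD28 and (182.6 − 50)/182.6 = 73% for SD6.

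**The case against.** The best defence is that this is a deliberate design for an exploratory pilot: at least four weeks of follow-up, then a roll-over study whose stated purposes include safety surveillance and drug elimination. Where that study cannot cover concentration monitoring, section 3.4 brings the patient back under this protocol, and section 8.10 allows AEs to be evaluated there. Drug may also be gone before SD56. All of this stands, and it confines the gap mainly to patients outside NI-0501-05 who still have measurable drug. It does not supply a recording rule for them.

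A reader might infer four stronger points, which the documents do not support:
- **That SAE collection stops at EoS.** The EoS limit is written for AEs only; the SAE period is ambiguous.
- **That late events have no route to the sponsor.** Sections 3.4 and 8.10 and the long-term study offer possible routes. What is missing is a stated rule.
- **That about 8.8 mg/kg will typically be present at SD56.** That figure needs the full ten infusions and linear elimination at the healthy-volunteer half-life. Section 5.3 expects faster clearance when IFNγ production is high.
- **That the healthy-volunteer zoster case, 14 days after 3 mg/kg, marks a level of risk.** One case sets no threshold, and patients here receive zoster prophylaxis.

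Section 8.8.1 does not simply end PK sampling at EoS either. Its sentence gives two end points.

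**Conclusion.** The concern holds as a mismatch between the recording rule and the monitoring rules. AE recording closes normally 28 to 50 days after the last dose, SAE reporting after a patient's own EoS is ambiguous, and the protocol requires infection searches for as long as drug is detectable. A new infection found in that interval has no recording rule in this study.

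The size is uncertain. At 22 days, 41% of the amount on board at the last dose remains after 28 days and 21% after 50. With faster clearance the interval may be short or absent. The conclusion does not rest on any one half-life, because the protocol itself plans for measurable drug after EoS. It is a correction worth making for the completeness of a named safety endpoint; it does not undermine the study's other results.

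**What to change.** - **10.3.1:** add that after the EoS visit, new infections, SAEs and related AEs are recorded until serum emapalumab is no longer detectable, either at the visits section 3.4 already requires or by transfer from NI-0501-05, and are shown in the CSR infection listing.
- **10.3.2:** state explicitly that SAE reporting covers the same period.
- **8.8.1 and 3.4:** reconcile the two on PK sampling after EoS, since undetectability is what ends prophylaxis and monitoring.
- **10.4.2:** align the pregnancy reporting period with the six-month contraception period in 4.1.1.

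The cost is a protocol amendment and CRF guidance. The visits and PCR searches are already required, and no dose or clinical rule changes. The downside is a later data cut, or an addendum listing, for some patients.
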